9.2 SAEs

The term "Serious Adverse Event" (SAE) is defined in 21 CFR 312.32 as follows:

"An adverse event or suspected adverse reaction is considered serious if, in the view of either the investigator or the sponsor, it results in any of the following outcomes:

- death,
- a life-threatening adverse event, inpatient hospitalization or prolongation of existing hospitalization,
- a persistent or significant incapacity or substantial disruption of the ability to conduct normal life functions,
- congenital anomaly/birth defect.

Important medical events that may not result in death, be life-threatening, or require hospitalization may be considered serious when, based upon appropriate medical judgment, they may jeopardize the patient or subject and may require medical or surgical intervention to prevent one of the outcomes listed in this definition. Examples of such medical events include allergic bronchospasm requiring intensive treatment in an emergency room or at home, blood dyscrasias or convulsions that do not result in inpatient hospitalization, or the development of drug dependency or drug abuse."

"Life-threatening" refers to an AE that, at occurrence, represents an immediate risk of death to the subject. Similarly, a hospital admission for an elective procedure is not considered an SAE.

9.2.1 Expedited reporting of adverse events to DAIDS

Requirements, definitions, and methods for expedited reporting of AEs are outlined in Version 2.0 (January 2010) of the *Manual for Expedited Reporting of Adverse Events* to DAIDS (DAIDS EAE Manual), which is available on the DAIDS Regulatory Support Center (RSC) website at https://rsc.niaid.nih.gov/clinical-research-sites/manual-expedited-reporting-adverse-events-daids.

The internet-based DAIDS Adverse Experience Reporting System (DAERS) must be used for EAE reporting to DAIDS. In the event of system outages or technical difficulties, EAEs may be submitted via the DAIDS EAE form at: https://rsc.niaid.nih.gov/clinical-research-sites/paper-eae-reporting.

For questions about DAERS, please contact [contact] or from within the DAERS application itself.

For questions about EAE reporting, please contact the DAIDS RSC Safety Office at [contact].

The SAE reporting category will be used throughout the study. After completion of the study, the Suspected Unexpected Serious Adverse Reaction (SUSAR) reporting category will be used if clinical staff becomes aware of an event on a passive basis.

The study products for which expedited reporting are required are:

- INO-6172,
- [Trimer 4571 + 3M-052-AF + Alum], and
- EP device.

There is no placebo product administered in this protocol. The NIAID/DAIDS will report all unexpected SAEs related to the study products observed in this clinical trial to the FDA, in accordance with 21 CFR 312.32 (IND Safety Reports).

9.3 Safety monitoring

9.3.1 **PSRT**

The PSRT comprises: DAIDS Medical Officer (MO) representative, Protocol Chair and Cochair, Protocol Team Leader (PTL), Clinical Safety Specialist (CSS), and Regional Medical Liaison (RML). The protocol team's clinic coordinator, clinical data manager, vaccine developer representative, clinical trial manager, and others may also be included in HVTN 305 PSRT meetings. The PSRT will review study safety information on a weekly basis through 2 weeks after the last participant receives the final study injection. Less frequent safety reviews will be conducted at the discretion of the PSRT.

9.3.2 HVTN Safety Monitoring Board

The Safety Monitoring Board (SMB) is a multidisciplinary group consisting of biostatisticians, clinicians, and experts in HIV vaccine research that, collectively, has experience in the conduct and monitoring of vaccine trials. Members of the SMB are not directly affiliated with the protocols under review.

The SMB reviews safety data (including cumulative reactogenicity events, AEs, laboratory safety data, and individual SAE reports) approximately every 4 months. The SMB conducts additional special reviews at the request of the HVTN 305 PSRT.

Study sites will receive SMB summary minutes and are responsible for forwarding them to their Institutional Review Board (IRB)/Ethics Committee (EC) and any applicable Regulatory Entity (RE).

9.4 Total blood volume

Required blood volumes per visit are shown in Appendix A and Appendix B. Not shown is any additional blood volume that would be required if a safety lab needs to be repeated or if a serum pregnancy test needs to be performed. The additional blood volume would likely be minimal. The total blood volume drawn for each participant will not exceed 500 mL in any 56-day (8-week) period, per American Red Cross guidelines for blood donation (https://www.redcrossblood.org/donate-blood/how-to-donate/eligibility-requirements.html).

9.5 Initial safety review

The trial will begin with enrollment in Group 1 only. Enrollment will be restricted to a maximum of 1 participant per day for the first 5 participants in Group 1. Enrollment will then be held. However, participants who have been enrolled will continue to receive vaccinations during the planned hold. The PSRT will review cumulative safety data reported through the visit scheduled 2 weeks post–enrollment. Upon PSRT determination that it is safe to proceed, full and unrestricted enrollments in all Groups may commence without restriction.

9.6 Safety pause and prompt PSRT AE review

The PSRT (see Section 9.3) will closely monitor participant safety. The trial can be paused at any time for any reason by the PSRT. When a trial is placed on safety pause, all enrollment and vaccination will be held until further notice. The AEs that will lead to a safety pause or prompt HVTN 305 PSRT AE review are summarized in Table 9-1. Vaccinations may be suspended for safety concerns other than those described in the table or before pause rules are met if, in the judgment of the HVTN 305 PSRT, participant safety may be threatened. Criteria for an individual participant's departure from the schedule of vaccinations are listed in Section 5.2.3.

Table 9-1 Pause rules

Event and relationship to study vaccine	Severity Grade	HVTN Site Actions	HVTN Core Action
SAE, related	5 or 4	Phone 24/7 Safety Phone immediately Email [contact] Submit CRFs immediately	Immediate pause
SAE, related	3, 2, or 1	Email CSS/RML Submit CRFs immediately	Prompt PSRT AE review to consider a pause
AE, related (see Grade 3 exceptions below)	4 or 3	Email CSS/RML Submit CRFs immediately	Prompt PSRT AE review to consider a pause

Exceptions to related Grade 3 AEs (for Grade-3 subjective reactogenicity events):

- Injection-site pain/tenderness
- Fatigue
- Generalized myalgia
- Generalized arthralgia
- Chills
- Headache
- Nausea (unless IV rehydration required)

Unrelated participant death: Sites will call the CSS/RML office phone upon learning of any unrelated participant deaths. The site will also email the CSS/RML and immediately submit CRFs. The CSS/RML will then promptly notify the PSRT.

If you need to contact the CSS/RML, refer to phone numbers and email addresses found on the HVTN 305 protocol home page on the HVTN Members' site at https://members.hvtn.org/protocols/hvtn305.

9.6.1 Plan for review of pause rules

For all safety pauses, HVTN Core notifies the HVTN 305 PSRT, HVTN Regulatory Affairs, DAIDS Pharmaceutical Affairs Branch (PAB), DAIDS Regulatory Affairs Branch (RAB), DAIDS Safety and Pharmacovigilance Team

(SPT), and participating HVTN CRSs. When an immediate safety pause is triggered, HVTN Core notifies the SMB.

Once a trial is paused, the HVTN 305 PSRT reviews safety data and decides whether the pause can be lifted or a permanent discontinuation of vaccination is appropriate, consulting the SMB if necessary. HVTN Core notifies the participating HVTN CRSs, HVTN Regulatory Affairs, DAIDS PAB, DAIDS RAB, and DAIDS SPT of the decision regarding resumption or discontinuation of study vaccinations. Based on the HVTN 305 PSRT assessment, DAIDS RAB notifies the FDA as needed.

If an immediate HVTN 305 PSRT notification or prompt HVTN 305 PSRT AE review is triggered, HVTN Core notifies the HVTN 305 PSRT as soon as possible during working hours (local time) or, if the information was received during off hours, by the morning of the next workday. If a prompt HVTN 305 PSRT AE review cannot be completed within 72 hours of notification (excluding weekends and US federal holidays), an automatic safety pause occurs.

The HVTN requires that each CRS submit to its IRB/EC and any applicable RE protocol-related safety information (such as IND safety reports, notification of vaccine holds due to the pause rules, unanticipated problems involving risks to participants or others, and notification of other unplanned safety pauses). CRSs must also follow all applicable RE reporting requirements.

9.7 Study termination

This study may be terminated early by the determination of the HVTN 305 PSRT, the NIH, the United States Department of Health and Human Services Office for Human Research Protections (OHRP), the FDA, or study product developers. In addition, the conduct of this study at an individual HVTN CRS may be terminated by the determination of the IRB/EC and any applicable RE.

9.8 Pregnancy

If a participant becomes pregnant during the course of the study, no more injections of study product will be given but remaining visits and study procedures, including AESI health contact, should be completed unless medically contraindicated or applicable regulations require termination from the study. During follow-up of persons who are confirmed pregnant, pregnancy testing is not required unless clinically indicated. If the participant terminates from the study prior to the pregnancy outcome, the site should make every effort to keep in touch with the participant in order to ascertain the pregnancy outcome. Pregnancies and pregnancy outcomes will be reported as described in the HVTN 305 SSP. If the participant is no longer pregnant, refer to Section 5.2.2.

10 Protocol conduct and informed consent

10.1 Protocol conduct

This research study will be conducted in the US and countries outside of the US, with funding from the NIH, among others. Due to this, the trial is subject to both US and local regulations and guidelines on the protection of human research subjects and ethical research conduct. Where there is a conflict in regulations or guidelines, the HVTN strives toward maximum protection of human research participants.

The study will comply with the International Council for Harmonization (ICH) Guideline for Good Clinical Practice (GCP E6 [R2]), HVTN and DAIDS policies and procedures as specified in the HVTN Manual of Operations and DAIDS Clinical Research Policies and Standard Procedures Documents, and all applicable regulatory requirements. These policies and procedures include protocol monitoring (on-site and remote) and compliance. DAIDS and HVTN policies and procedures are available for review by any IRB/EC/RE upon request. Any policies or procedures that vary from DAIDS and HVTN standards or require additional instructions (eg, instructions for randomization specific to this study) will be described in the HVTN 305 SSP. Regarding protocol registration, sites should follow procedures outlined in the current version of the DAIDS Protocol Registration Manual.

HVTN scientists and operational staff are committed to substantive community input into the planning, conduct, and follow-up of its research, ensuring that locally appropriate cultural and linguistic needs of study populations are met. Community Advisory Boards (CABs) are required by DAIDS and supported at all HVTN research sites to ensure community input in accordance with Good Participatory Practices (GPP).

10.2 Compliance with NIH guidelines for research involving products containing recombinant or synthetic nucleic acid molecules

Because this study is evaluating products containing recombinant or synthetic nucleic acid molecules and is funded by the NIH, it must comply with regulations set forth in the NIH's *Guidelines for Research Involving Recombinant or Synthetic Nucleic Acid Molecules* (April 2019). Information about the study must be submitted to the Institutional Biosafety Committee (IBC) for each CRS. Investigators at each CRS are responsible for obtaining IBC approval per NIH guideline *Section IV-B7-a-(1)*. IBC review and approval must be documented by the investigator and submitted as part of DAIDS's initial protocol registration for this trial before participants are enrolled at the CRS. If this protocol is amended, investigators should follow the requirements of their respective IBC.

10.3 Informed consent

The sample informed consent form (SICF) in Appendix D describes the investigational vaccine and all aspects involved in study participation. Documentation of appropriate informed consent must be in place prior to conducting study procedures with participants. Periodic assessment of participants' continued understanding of key study concepts and informed consent must also be documented. Study sites are strongly encouraged to have their local CABs review their site-specific consent forms. This review should include, but should not be limited to, issues of cultural competence, local language considerations, and the SICF's level of comprehensibility.

If any new information is learned that might affect the participants' decisions to stay in the trial, this information will be shared with them. If necessary, participants will be asked to sign revised informed consent forms.

An HVTN CRS may employ recruitment efforts prior to the participant consenting. For example, some HVTN CRSs use a telephone script to prescreen people before they come to the clinic for a full screening visit. Participants must sign a screening or protocol-specific consent before any procedures are performed to determine eligibility. HVTN CRSs must submit recruitment and prescreening materials to their IRB/EC and any applicable RE for human subjects protection review and approval.

10.3.1 Screening consent form

Without a general screening consent, screening for a specific study cannot take place until the site receives protocol registration from the DAIDS RSC Protocol Registration Office. Sites should follow procedures outlined in the current version of the DAIDS Protocol Registration Manual.

Some HVTN CRSs have approval from their IRB/EC and any applicable RE to use a general screening consent form that allows screening for an unspecified HIV vaccine trial. In this way, HVTN CRS staff can continually screen potential participants and, when needed, proceed quickly to obtain protocol-specific enrollment consent. Sites conducting general screening or prescreening approved by their IRB/EC and any applicable RE may use the results from this screening to determine eligibility for this protocol, provided that the tests are conducted within the time periods specified in the eligibility criteria.

11 Exploratory studies

Samples may be used for other testing and research related to furthering the understanding of HIV immunology or vaccines. In addition, cryopreserved samples may be used to perform additional assays to support standardization and validation of existing or newly developed methods.

Only genetic testing that is in accordance with the language in the SICF (Appendix D) may be performed on samples.

11.1 Specimen storage and other use of specimens

The HVTN stores specimens from all study participants indefinitely unless a participant requests that specimens be destroyed or if destruction or a time limit for storage is required by IRB/EC or RE.

"Other use" of specimens is defined as "studies not covered by the protocol or the informed consent form for the main study" (see Appendix D).

This research may relate to HIV, vaccines, the immune system, or other diseases. This could include genetic testing and, potentially, genome-wide studies. This research is done only to the extent authorized in each study site's informed consent form or as otherwise authorized under applicable law. Other research on specimens ("other use") will occur only after review and approval by the HVTN, the IRB/EC of the researcher requesting the specimens, and the IRBs/ECs/REs of the CRSs, if required.

As part of consenting for the study, participants will document their initial decision to allow or not allow their specimens to be used in other research, and they may change their decision at any time. The participant's initial decision about other use of their specimens, and any later change to that decision, is recorded by their CRS in an internet-based tool that documents participants' current decisions for other use of their specimens. The HVTN will only allow other research to be done on specimens from participants who allow such use.

CRSs must notify HVTN Regulatory Affairs if institutional or local governmental requirements pose a conflict with or impose restrictions on specimen storage or other use of specimens.

12 Literature cited

Appendix A Schedule of procedures: Participants undergoing FNA

	Number	01	02	03	04	05	06	07	08	09	10	11	12	AESI ¹⁸
Stud		0	2	4	6	7	12	14	15	24	26	52	78	
Study		0	0.5	1	1.5	1.75	3	3.5	3.75	6	6.5	12	18	
	udy Day	-56 to 0	1	15	29	43	50	85	99	106	169	183	365	547
	ocedure	Screen ¹	Vac 1		Vac 2		FNA	Vac 3		FNA	Vac 4 ¹⁷			
Study procedures														
Assessment of Understanding		√												
Informed consent		√												
Medical history ²		√												
Physical exam ³		√	√	√	√	√		√	√		√	√	√	
Contraception status assessment ⁴		√	√		√			√			√			
Social impact assessment			√	√	√	√		√	√		√	√	√	
Social impact questionnaire					√			√					√	
Risk-reduction counseling ⁵		√	√	√	√	√		√	√		√	√	√	
Concomitant medications ⁶		√	√	√	√	$\sqrt{7}$	√	√	$\sqrt{7}$	√	√	√	V	
Adverse Events (AEs)			√	√	√	√		√	√		√	√		
AESIs/MAAEs/SAEs			√	√	√	√		√	√		√	√	V	√
Vaccination ⁸			√		√			√			√			
Reactogenicity assessment ⁹			√		√			√			√			
EP injection site assessment				√	√	√	√	√	√	√	√	V	√	$\sqrt{18}$
Clinical labs	Tube													
Pregnancy test (urine or serum) 10,11		√	√		√		√	√	√	√	√			
HBsAg/anti-HCV ¹¹	SST	5												
HIV screening test ^{11,12}	SST	5												
Calcium ¹¹	SST	5												
CBC/Differential ¹¹	EDTA	5		5		5			5			5		
ALT & Creatinine ¹¹	SST	5		5		5			5			5		
HIV diagnostic test	EDTA							10				10	20	
Research samples ¹³														
PBMC for assays & storage	ACD			42.5		136		13614				136	178.5	
Serum for assays and storage	SST	34		34		34			34			34	34	
Leukapheresis ¹⁵		√							√					
Fine Needle Aspiration ¹⁶							√			√				
Daily volu	me (mL)	59	0	86.5	0	180	0	146	44	0	0	190	232.5	
56-day total volu				145.5	145.5	325.5	325.5	326	370	370	0	190	232.5	

Green shading: Vaccination visit for all groups; **Blue shading:** Vaccination visit for Group 3 only.

- ¹ Screening evaluations at Visit 01 are performed no more than 56 days before Day 1.
- ² Medical history: A complete medical history is performed during screening. At enrollment and at subsequent visits, an interim medical history may be performed.
- ³ A complete **physical exam** is performed at screening and last clinic visit to include height, weight, and vital signs, and clinical assessments of head, ears, eyes, nose, and throat; neck and lymph nodes; heart; chest; abdomen; extremities; neurological function; and skin. At other visits, a **targeted physical exam** will be performed as needed, based on participant reports or indications of illness
- ⁴ Contraception status assessment is required only for participants who were assigned female sex at birth and are capable of becoming pregnant. Participants will also be provided with counselling about contraception.
- ⁵ Risk-reduction counseling per CRS Standard Operating Procedures (SOP).
- ⁶ Concomitant medications, including prescription and nonprescription drugs, vitamins, topical products, alternative/complementary medicines, recreational drugs, vaccinations, and allergy shots, are recorded during screening, at enrollment, and at each subsequent clinic visit.
- ⁷ During concomitant medications check-in participant is counseled to avoid medications that would increase the risk of bleeding for 7 days prior to FNA (see Section 8.5).
- ⁸ Vaccination (in-clinic assessments): At least 60 minutes after the first vaccination and after the fourth vaccination, and 30 minutes after for all other vaccinations. Prior to clinic discharge, the injection site and systemic symptoms will be assessed, and participants will have vital signs taken.
- 9 Reactogenicity: Clinic staff will follow new or unresolved reactogenicity symptoms present at the final reactogenicity day (see Section 8.3 and HVTN 305 SSP)
- 10 Pregnancy test: For participants assigned female sex at birth. Pregnancy test may be performed on blood specimens. Persons who are NOT capable of becoming pregnant due to total hysterectomy or bilateral oophorectomy (verified by medical records) or menopause (no menses for ≥ 1 year) are not required to undergo pregnancy testing. For persons who are confirmed pregnant, pregnancy testing is not required unless clinically indicated.
- ¹¹ Local labs may assign appropriate alternative tube types for locally performed tests.
- ¹² HIV screening test: See Section 5.1.1.
- ¹³ **Research samples:** Blood-draw volumes for each tube type shown. Alternate tube types may be used under certain conditions (eg, product shortages) upon approval of the HVTN Laboratory Center. Refer to the Specimen Collection SSP for more information.
- ¹⁴ Blood draw will be performed before vaccination.
- ¹⁵ **Leukapheresis:** May be performed prior to enrollment visit once the participant has been found to have met all protocol enrollment criteria (see Section 5.1.1 and 5.1.2) and leukapheresis eligibility criteria (see Section 8.6).
- ¹⁶ Fine Needle Aspiration: Target for FNA is 3 weeks post–second and –third vaccinations.
- ¹⁷ Vaccination 4/Visit 10 will be conducted only for participants assigned to Group 3.
- ¹⁸ **AESI contact:** CRS staff will contact study participants at month 18 to collect the information listed in Section 8.10. The EP-injection–site assessment will be an abbreviated questionnaire that can be conducted over phone.

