*Up to 9 additional participants may be enrolled (for a total of up to 54), if needed, to have approximately 45 participants contribute to immunogenicity analyses. Specific scenarios that could necessitate enrollment of additional participants in order to prevent loss of statistical power of the study include, but are not limited to, the following: loss of participants due to moving, withdrawal of consent, missing vaccine visits, inability to complete FNA, or variations in the clinical care due to unpredictable events. Participants will not be replaced after completion of visit 6, the first FNA visit.

** Initial enrollment will be restricted to 1 participant per day for the first 5 participants in Group 1, and enrollment will pause after the first 5 participants are enrolled in Group 1. The Protocol Safety Review Team (PSRT) will review cumulative safety information for these first 5 participants recorded through the visit scheduled 2 weeks post–first vaccination and will determine whether it is safe to proceed with full enrollment in all groups.

[†]For the first five participants in Group 3, the Month 3 vaccination will be limited to 1 participant per day.

§FNA will not be conducted for Group 1 but may be optional for Groups 2 and 3 and will be offered to participants during screening. A minimum target of 9 participants in these groups will be asked to provide consent for receiving the FNA.

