5.2.4 Discontinuation of study participation

A participant may be discontinued from protocol participation for the following reasons:

- Participant voluntarily withdraws;
- CRS determines the participant is lost to follow-up;
- The investigational new drug (IND) application sponsor or regulatory authorities stop the study; or,
- PI assessment that it is not in the best interest of the participant to continue participation in the study or that the participant's compliance with the study is not sufficient.

If a participant terminates participation in the study early for any reason, the site PI should consider if the following assessments are appropriate: end-of-study HIV test, complete blood count (CBC with differential, serum chemistry [ALT and creatinine], physical examination, and if indicated, a pregnancy test [see Appendix A and Appendix B]). For participants living with HIV, please see

Section 8.8. If the site PI has questions regarding a termination visit, they should consult with the PSRT.

6 Statistical considerations

This phase-1 study will target recruiting a total of 45 adult participants without HIV aged 18 to 55 years.

In Group 1, a total of approximately 9 participants will receive 3 administrations of sD-NP-GT8 DNA at a dose of 0.4 mg, coformulated with IL-12 DNA at a dose of 0.1 mg at days 1, 29, and 85. Study products will be administered intradermally via EP of the skin on each upper arm.

In Group 2, a total of approximately 18 participants will receive 3 administrations of sD-NP-GT8 DNA at a dose of 1.6 mg, coformulated with IL-12 DNA at a dose of 0.4 mg at days 1, 29, and 85. Study products will be administered intradermally via EP of the skin on each upper arm.

In Group 3, a total of approximately 18 participants will receive 3 administrations of sD-NP-GT8 DNA at a dose of 1.6 mg, coformulated with IL-12 DNA at a dose of 0.4 mg at days 1, 29, and 85. These doses will be administered intradermally via EP of the skin on each upper arm. All participants in Group 3 will also receive 2 administrations of Trimer 4571 at a dose of 100 mcg adjuvanted with 5 mcg of 3M-052-AF + 500 mcg Alum via IM injections into the deltoid muscle at days 85 and 169.

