6.1 Sample size justification and accrual

The protocol team will convene after the final enrolled participant has completed Visit 6 (first FNA visit) to determine if further participants should be enrolled to ensure adequate samples for immunogenicity analysis. Examples of reasons that might necessitate enrollment of additional participants are provided in Section 1.5. If some participants of the original 45 enrolled will not contribute data to some of the immunogenicity analyses, the protocol team may enroll up to 9 additional fully evaluable participants, or a total of 54 participants enrolled, with the goal of 45 contributing to the final immunogenicity analyses. Participants will not be replaced after completion of visit 6, the first FNA visit.

Every study participant will be followed up for an AESI contact at month 18.

Details about the pace of enrollment can be found in Section 1.5.

Since enrollment is concurrent with receiving the first vaccination, all participants will provide some safety data. However, for immunogenicity analyses, data may be missing for a variety of reasons, including participants terminating from the study early, problems in shipping specimens, or high assay background. Immunogenicity data from 17 phase 1, 2, and phase 2a HVTN vaccine trials, which began enrolling after June 2005 (data as of September 2014), indicate that 17% is a reasonable estimate for the rate of missing data. Therefore, the sample-size calculations in Section 6.1.1 below account for about 17% of enrolled participants having missing data.

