8.3 Reactogenicity assessments

Reactogenicity definition: Signs and symptoms considered to represent reactogenicity from the vaccine include systemic events of increased body temperature, fatigue, generalized myalgia, generalized arthralgia, headache, chills, nausea, and local events at the injection site, including pain/tenderness, induration, and erythema.

The reactogenicity assessment period is the day of vaccination and 7 full days following vaccine administration for INO-6172 alone and 14 full days following vaccine administration for INO-6172 along with Trimer 4571 adjuvanted with 3M-052-AF/Alum and Trimer 4571 alone, adjuvanted with 3M-052-AF/Alum. Clinicians will follow and collect resolution information for any reactogenicity signs and symptoms that have not resolved within the reactogenicity assessment period.

Prevaccine administration: Medical history and evaluations, including vital signs and planned injection-site evaluations, are performed as described in Appendix A and Appendix B

Postvaccine administration in-clinic evaluation: Following the first vaccine administration of sD-NP-GT8, participants will be observed for a minimum of 60 minutes postadministration. For all subsequent injections, participants will be observed for a minimum of 30 minutes with the following exception: for Group 3, participants will be observed for 60 minutes postadministration of Trimer 4571 + 3M-052-AF + Alum. During this time, vital signs will be recorded, the injection site will be inspected for evidence of local reaction, and any evidence of systemic symptoms will be assessed.

Postvaccine administration contact with participant: Remote or in-person contact between the participant and the site staff should take place at least once on the third or fourth day following vaccination. Any postvaccination reaction that is Grade 2 or higher will be assessed by a clinician within 48 hours after onset unless the reaction is improving and/or has completely resolved. Additionally, other clinical concerns may prompt a study visit based on the judgment of a study clinician.

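### The schedule footnotes allow Group 3 to leave 30 minutes after the first Trimer dose, where Section 8.3 requires 60 minutes

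*Protocol*

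**What the plan says.** Three places in the Protocol set the observation time after injection.

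- **Section 8.3** requires at least 60 minutes after the first DNA administration and at least 30 minutes after later injections, with one exception: "for Group 3, participants will be observed for 60 minutes postadministration of Trimer 4571 + 3M-052-AF + Alum". The exception is tied to the product and is not limited to one dose.
- **Appendix A, footnote 8** (participants having FNA): "At least 60 minutes after the first vaccination and after the fourth vaccination, and 30 minutes after for all other vaccinations".
- **Appendix B, footnote 7** (participants not having FNA) gives the same rule in the same words.

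On dosing, Section 6 says of Group 3: "All participants in Group 3 will also receive 2 administrations of Trimer 4571 at a dose of 100 mcg", on Days 85 and 169. Sections 1.5, 7.1 and 7.4.2 agree, giving months 3 and 6. These are vaccinations 3 and 4. Appendix A, footnote 17, adds: "Vaccination 4/Visit 10 will be conducted only for participants assigned to Group 3".

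**The concern.** The footnotes sort visits by vaccination number, while Section 8.3 sorts them by product. The two agree only if the footnotes give 60 minutes at every vaccination that includes Trimer. They do so at vaccination 4 but leave vaccination 3 in the 30-minute group, with no exception for Group 3.

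Section 8.7 sends sites to Appendices A and B for what is done at each visit, so clinic staff may well work from the footnotes. A site that applied only the footnote minimum could discharge a Group 3 participant 30 minutes before Section 8.3 allows and believe that it had complied. This would happen at the participant's first dose of adjuvanted Trimer, given at the same visit as the third DNA dose.

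The stake is immediate supervision for acute reactions. Table 2-3 lists allergic reaction, up to anaphylaxis, as uncommon or rare across the study products. The documents give no data on reactions between 30 and 60 minutes, so the point rests on the Protocol's own 60-minute requirement and not on evidence of excess risk in that interval.

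**Working it through.** **Step 1. Compare the rules by group and vaccination.** Minimum minutes of observation:

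| Group | Vaccination | Product | Section 8.3 | Footnotes |
|---|---|---|---|---|
| 1 and 2 | 1 | DNA | 60 | 60 |
| 1 and 2 | 2 | DNA | 30 | 30 |
| 1 and 2 | 3 | DNA | 30 | 30 |
| 3 | 1 | DNA | 60 | 60 |
| 3 | 2 | DNA | 30 | 30 |
| 3 | **3 (Day 85, Visit 07)** | DNA + Trimer | **60** | **30** |
| 3 | 4 (Day 169, Visit 10) | Trimer | 60 | 60 |

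There is exactly one mismatch.

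**Step 2. Ask whether the difference could be intended.** Only Group 3 has vaccination 4, so the footnotes' 60 minutes there matches the Trimer exception. Nothing in the documents gives a reason for less observation at the first Trimer dose than at the second. Elsewhere the plan treats the two doses alike or is more careful at the first. The Section 8.3 symptom diary runs 14 full days after each of them, and the notes to Table 1-1 say: "For the first five participants in Group 3, the Month 3 vaccination will be limited to 1 participant per day". An omission is the natural reading.

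**Step 3. Look for a text that settles it.** The reactogenicity footnote next to the observation footnote cites Section 8.3 and the study-specific procedures, but for follow-up of unresolved symptoms and not for observation time. The version history lists no change to observation time. The SAP does not address it. No section available for review says which text prevails; the study-specific procedures were not available.

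**Step 4. Size at planned enrollment.** Group sizes of 9, 18 and 18 are from Table 1-1.

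- Vaccination visits: 9 × 3 + 18 × 3 + 18 × 4 = 27 + 54 + 72 = 153.
- Trimer visits: 18 × 2 = 36.
- Visits under conflicting minimums: 18 × 1 = 18.
- Shares: 18/36 = 50% of Trimer visits; 18/153 = 11.8% of vaccination visits.

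**Step 5. Upper scenario.** Section 6 gives Group 3 as approximately 18, and Section 6.1 says "the protocol team may enroll up to 9 additional fully evaluable participants, or a total of 54 participants enrolled" without a split between groups. Assume that all 9 enter Group 3 and that everyone completes the regimen.

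- Group 3: 18 + 9 = 27.
- Vaccination visits: 27 + 54 + 27 × 4 = 189.
- Trimer visits: 27 × 2 = 54.
- Shares: 27/54 = 50%; 27/189 = 14.3%.

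**The case against.** The strongest reply is that the texts can be followed together. The footnotes state a floor, Section 8.3 states a longer time for a named group and product, and 60 minutes satisfies all of them. On this view the safeguard is already in the Protocol body and the footnotes are incomplete summaries. That is correct as far as it goes, but it protects only participants at sites that notice Section 8.3. The footnotes still state a minimum below what the Protocol requires, in the schedule that sites are told to use.

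A second reply is that the consequence is small, and this largely stands. The closest experience in the Protocol reports no related SAEs: BG505 SOSIP.664 with 3M-052-AF, a 300-mcg chimeric trimer with the same adjuvant dose, and Trimer 4571 with Alum. Those groups are small and no results are given by observation window, so they neither show that 30 minutes is enough nor support a larger concern. Even under the footnotes, the injection site, systemic symptoms and vital signs are checked before discharge, and the contact on day 3 or 4 and the 14-day diary follow.

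The 27-participant scenario is also fairly questioned. Extra enrollment is prompted largely by losses or missed visits, which sits awkwardly with full completion. It is a bound under stated assumptions; the working figure is about 18.

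Finally, the study-specific procedures might give sites the right time. That cannot be checked here, and it would not make the footnotes correct.

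**Conclusion.** The inconsistency holds. For Group 3 at Visit 07, Section 8.3 requires 60 minutes and both schedule footnotes set a minimum of 30. At planned enrollment it concerns about 18 participants, one visit each. Under the assumptions in the upper scenario it would be 27. The number actually affected is smaller if participants stop before vaccination 3 or if sites observe for longer than the footnote minimum.

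The conclusion rests on reading the Section 8.3 exception as covering both Trimer doses. The section does not say so in terms, but it sets no limit to one dose. The effect is on participant supervision only: reactions would still be recorded, and no endpoint, sample size, power figure or analysis changes. It should be fixed because it is a wrong safety minimum in an operative schedule and is simple to correct.

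**What to change.** Leave Section 8.3 unchanged. Amend Appendix A footnote 8 and Appendix B footnote 7 to require at least 60 minutes after vaccination 1 in all groups; at least 60 minutes after vaccinations 3 and 4 in Group 3, that is, after each administration of Trimer 4571 + 3M-052-AF + Alum; and at least 30 minutes after every other vaccination.

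This takes two footnote edits, by clarification memo or letter of amendment. Measured against Section 8.3 it adds no clinic time, because the 60 minutes is already required. Measured against the footnote minimum it adds up to 60 − 30 = 30 minutes per Group 3 participant at one visit: 18 × 30 = 540 minutes (9 hours) in total at planned enrollment, or 27 × 30 = 810 minutes (13.5 hours) if all 9 additional participants entered Group 3.
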